5. SUBJECT ENROLLMENT

Before subjects begin participation in any study-specific activities/procedures, Amgen requires a copy of the site's written institutional review board/independent ethics committee (IRB/IEC) approval of the protocol, informed consent form, and all other subject information and/or recruitment material, if applicable (see [Section 11.2](#)).

All subjects or legally acceptable representatives must personally sign and date the Amgen approved informed consent form before commencement of study-specific activities/procedures.

A subject is considered enrolled when the investigator decides that the subject has met all Part 1 eligibility criteria. The investigator is to document this decision and date, in the subject's medical record and in/on the enrollment case report form (CRF).

Each subject who enters into the screening period for the study (defined as the point at which the subject or subject's legally acceptable representative signs the informed consent form) receives a unique subject identification number before any study-related activities/procedures are performed. This number will be used to identify the subject throughout the clinical study and must be used on all study documentation related to that subject. The subject identification number must remain constant throughout the entire

clinical study; it must not be changed after initial assignment, including if a subject is rescreened.

Subjects not meeting Part 1 eligibility criteria are permitted to rescreen 1 additional time after failing the first screening.

Part 2 eligibility criteria will be evaluated at any time after enrollment through the 24-month run-in period at the time when MRD status becomes positive (see [Section 4.2](#)). Subjects who do not meet Part 2 eligibility criteria will end the study.

5.1 Treatment Assignment

Subjects who meet Part 2 eligibility criteria will be assigned to treatment with blinatumomab.

The treatment assignment date is to be documented in the subject's medical record and on the enrollment CRF.

6. TREATMENT PROCEDURES

6.1 Classification of Product(s), Medical Device(s) and/or Combination Product(s)

The Amgen Investigational Product used in this study includes: blinatumomab. Non-investigational medical device(s) (ie, medical device[s] not under study) will be described in [Section 6.6](#).

The Investigational Product Instruction Manual (IPIM), a document external to this protocol, contains detailed information regarding the storage, preparation, destruction, and administration of blinatumomab.

6.2 Investigational Product

6.2.1 Amgen Investigational Product Blinatumomab

Blinatumomab will be manufactured and packaged by Amgen Inc. and distributed using Amgen clinical study drug distribution procedures.

Blinatumomab will be supplied in a single-use glass injection vials as a sterile, preservative-free, white to off-white, lyophilized powder for reconstitution and administration by continuous IV infusion. Each vial contains blinatumomab with additional excipients and buffers including citric acid monohydrate, trehalose dihydrate, lysine hydrochloride and polysorbate 80, pH 7.

To prepare blinatumomab for IV infusion, the lyophilized powder is reconstituted with sterile water for injection. The reconstituted solution is added to an infusion bag containing 0.9% NaCl and a product-specific stabilizer (IV Solution Stabilizer). The

IV Solution Stabilizer functions to prevent adsorption of blinatumomab to surfaces of the infusion components. The IV Solution Stabilizer is supplied in 10 mL single-use glass injection vials as a sterile, preservative-free, clear, colorless-to-slightly-yellow liquid concentrate.

Sterile water for injection and supplies required for reconstitution and injection of blinatumomab will not be provided to clinical sites.

For information surrounding the use of a continuous infusion pump, refer to [Section 6.6 Medical Devices](#).

6.2.1.1 Dosage, Administration, and Schedule

Blinatumomab will be administered as a continuous IV infusion.

Cycle 1 of blinatumomab treatment is 12 weeks (84 days) in duration and includes 8 weeks (56 days) of blinatumomab IV infusion followed by a 4-week (28-day) treatment-free interval.

The initial dose of blinatumomab will be 9 µg/day for the first 7 days of treatment. Blinatumomab dose will then be escalated (dose-step) to 28 µg/day starting on day 8 (week 2), followed by a dose-step up to 112 µg/day starting on day 15 (week 3) and continuing until completion of therapy (day 57 for cycle 1).

To evaluate disease status, MRD status (CT-DNA) will be assessed at cycle 1 day 1 prior to blinatumomab infusion, on cycle 1 days 15 and 43, the end of the blinatumomab infusion (day 57), and 2 weeks after the end of the blinatumomab infusion (day 71 + 3 days). A PET-CT will be performed only if subject remains MRD-positive at the day 57 assessment or has clinical signs and symptoms of disease progression.

Prior to initiation of blinatumomab and each dose-step escalation, dexamethasone will be administered as described in [Table 2](#).

The daily blinatumomab dose may be up to 10% lower or higher in order to account for possible pump inaccuracies. A dose of up to 10% higher than the intended dose may not require specific intervention. The effects of overdose of blinatumomab are not known. In case of overdose or medication error, the infusion should be immediately stopped. Consultation with the Amgen medical monitor is strongly recommended for prompt reporting of clinically apparent or laboratory adverse events possibly related to overdose. If the overdose results in an adverse event, the subject should be followed carefully until all signs of toxicity are resolved, and consultation with the Amgen medical

monitor is also strongly recommended even if there are no adverse events, in order to discuss the minimal duration of dose interruption. The adverse event(s) should be recorded/reported per [Section 9](#). Resumption of blinatumomab should adhere to the Dosage Adjustments, Delays, Rules for Withholding or Restarting, Permanent Discontinuation [Section 6.2.1.2](#).

The dosing, start and stop date and time, and lot number of blinatumomab is to be recorded on each subject's CRF.

6.2.1.1.1 Inpatient Dosing

Subjects should be monitored in a hospital for a minimum of 72 hours following initiation of therapy and for a minimum of 48 hours at each dose-step increase because of the potential adverse events associated with T-cell distribution and potential cytokine release effects triggered by the administration of blinatumomab. Nurses/physicians trained in emergency medicines should be available for immediate intervention in case of complications.

6.2.1.1.2 Outpatient Dosing

After a subject meets the minimum criteria for inpatient administration and monitoring as described above, and if subject is deemed stable by the investigator, administration of blinatumomab IV infusion may continue as an outpatient. See [Section 6.2.1.2.1](#) regarding monitoring following dose interruptions.

In the outpatient setting, either the subject will return to the study site for changes of infusion bag or the subject will be visited by a well-trained ambulatory home-care service provider at specific intervals to change the infusion bag. The subject and the home health care provider will be trained and will receive written instructions for storage of the IV bags. For the home health care provider study-specific requirements and recording source documentation must be completed before any study-related tasks are started. A comprehensive list of all home health care services, including but not limited to the storage, handling, and administration of blinatumomab, as well as mandatory procedural and data collection requirements, will be separately provided in a home health care manual. Following each visit, this information will be documented on the home health care services visit worksheet and forwarded to the investigator. In case of any adverse event in the outpatient setting, the home health care provider should directly contact the investigator at the study center for further management. Any unexpected or unusual events, as well as deviations, will be communicated promptly to the investigator. The home health care professionals provide 24-hour emergency on-call service. In addition,

the subject will visit the study site for the examinations according to the schedule of assessments ([Table 4](#)).

6.2.1.2 Dosage Adjustments, Delays, Rules for Withholding or Restarting, Permanent Discontinuation

6.2.1.2.1 Infusion Interruption Due to Technical/Logistical Reasons

The administration of blinatumomab should not be interrupted, if possible. In case of infusion interruption due to any technical or logistic reason, the interruption should be as short as possible and the infusion continued at the earliest time possible. Every interruption longer than 1 hour should be documented. If the interruption is longer than 4 hours, restart of the infusion should be performed in the hospital, under the supervision of the investigator. The subject should be observed overnight for possible side effects after the restart. Administration of dexamethasone premedication prior to resumption of blinatumomab infusion after a treatment interruption of more than 4 hours is described in [Table 2](#).

The reason for dose change of blinatumomab is to be recorded on each subject's CRF.

6.2.1.2.2 Infusion Interruptions/Dose Modifications Due to Adverse Events

Table 1. Infusion Interruptions/Dose Modifications Due to Adverse Events

Toxicity	Grade or Adverse Event	Instructions for Treatment Interruption and Restart
Cytokine Release Syndrome	3	
 Interrupt blinatumomab until the event improves to grade ≤ 1 and administer corticosteroids (refer to Table 2) Restart no less than 72 hours after the initial observation of the grade 3 event at the following dose levels: 
 If event occurred at 112 $\mu\text{g}/\text{day}$, resume at 28 $\mu\text{g}/\text{day}$ If event occurred at 9 or 28 $\mu\text{g}/\text{day}$, resume at 9 $\mu\text{g}/\text{day}$ Escalate up 1 dose level after 7 days if toxicity does not reoccur. Increase dose stepwise at 7-day intervals to target dose of 112 $\mu\text{g}/\text{day}$ if toxicity does not reoccur. Permanently discontinue if: 
 Initial grade 3 CRS does not improve to grade ≤ 1 within 7 days, OR Grade 3 CRS reoccurs at the lower dose level within 7 days of reinitiation OR Grade 3 CRS reoccurs at a dose of 9 $\mu\text{g}/\text{day}$ without prior dose-step escalation
	4	
 Permanently discontinue blinatumomab
Neurologic Events	3	
 Interrupt blinatumomab until the event improves to grade ≤ 1 and administer corticosteroids (refer to Table 2) Restart no less than 72 hours after the initial observation of the grade 3 event at the following dose levels: 
 If event occurred at 112 $\mu\text{g}/\text{day}$, resume at 28 $\mu\text{g}/\text{day}$ If event occurred at 28 $\mu\text{g}/\text{day}$, resume at 9 $\mu\text{g}/\text{day}$ Escalate up 1 dose level after 7 days if toxicity does not reoccur. Increase dose stepwise at 7-day intervals to target dose of 112 $\mu\text{g}/\text{day}$ if toxicity does not reoccur. Permanently discontinue if: 
 Initial grade 3 neurologic event occurred at 9 $\mu\text{g}/\text{day}$, OR Initial grade 3 neurologic event does not improve to grade ≤ 1 within 7 days, OR Grade 3 neurologic event reoccurs at the lower dose level within 7 days of re-initiation, OR Grade 3 neurologic event reoccurs at a dose of 9 $\mu\text{g}/\text{day}$
	4	
 Permanently discontinue blinatumomab
	Seizure ^a	
 Interrupt blinatumomab, administer corticosteroids (refer to Table 2) and anti-seizure medication per local practice For restart, refer to grade 3 neurologic events above for dose level rules for re-instituting infusion Do not re-initiate blinatumomab until 7 days after the last seizure and after therapeutic levels of anti-seizure medication are likely to have been achieved Permanently discontinue if a second seizure occurs with re-initiation of blinatumomab at any dose

Footnotes defined on last page

Table 1. Infusion Interruptions/Dose Modifications Due to Adverse Events

Toxicity	Grade or Adverse Event	Instructions for Treatment Interruption and Restart
Elevated liver enzymes	NA	
 • Interrupt blinatumomab (refer to Table 3) if any one of the following occurs: 
 ○ TBL > 3 x ULN at any time ○ ALP > 8 x ULN at any time ○ AST or ALT > 8x ULN at any time ○ AST or ALT > 5x ULN but < 8 x ULN for ≥ 2 weeks ○ AST or ALT > 3 x ULN with clinical signs or symptoms that are consistent with hepatitis (eg, RUQ abdominal pain/tenderness, fever, nausea, vomiting, jaundice) • Permanently discontinue blinatumomab if: 
 ○ TBL > 2 x ULN OR INR > 1.5 (for subjects not on anticoagulant therapy) AND ○ AST or ALT > 3 x ULN (when baseline was < ULN) AND ○ no other cause for the combination of the above laboratory abnormalities is immediately apparent 
Refer to Section 6.4 for additional details

Other clinically relevant adverse events	3	
 • Interrupt blinatumomab until event improves to grade ≤ 1 (refer to Table 2) • Restart no less than 72 hours after the initial observation of the grade 3 event at the following dose levels: 
 ○ If event occurred at 112 µg/day, resume at 28 µg/day ○ If event occurred at 9 or 28 µg/day, resume at 9 µg/day • Escalate up 1 dose level after 7 days if toxicity does not reoccur. Increase dose stepwise at 7-day intervals to target dose of 112 µg/day if toxicity does not reoccur. • Permanently discontinue blinatumomab if: 
 ○ Initial grade 3 event does not improve to grade ≤ 1 within 14 days, OR ○ Grade 3 event reoccurs at the lower dose level within 7 days of re-initiation OR ○ Grade 3 event reoccurs at a dose of 9 µg/day without prior -dose-step escalation
	4	
 • Permanently discontinue blinatumomab

Page 2 of 2

ALP = alkaline phosphatase; ALT = alanine aminotransferase; AST = aspartate aminotransferase; CRS = cytokine release syndrome; NA = not applicable; TBL= total bilirubin; ULN = upper limit of normal; MRI = magnetic resonance imaging

Grade scale is based on Common Terminology Criteria for Adverse Events version 4.0.

^a Obtain brain MRI and perform cerebro spinal fluid (CSF) analysis, if there are no contraindications

Restart of an infusion after interruption for an adverse event should be performed under supervision of the investigator. Before blinatumomab is restarted, premedication with dexamethasone must be administered as described in [Table 2](#).

6.2.1.3 Permanent Discontinuation of Blinatumomab

Blinatumomab will be permanently discontinued for:

Disease Progression

Cytokine Release Syndrome

- Initial grade 3 CRS that does not improve to grade ≤ 1 within 7 days
- Grade 3 CRS that reoccurs at the lower dose level within 7 days of reinitiation
- Grade 3 CRS reoccurs at a dose of 9 $\mu\text{g}/\text{day}$ without prior dose-step escalation
- Grade 4 CRS

Neurologic Events

- Initial grade 3 neurologic event occurred at 9 $\mu\text{g}/\text{day}$
- Initial grade 3 neurologic event does not improve to grade ≤ 1 within 7 days
- Grade 3 neurologic event that reoccurs at the lower dose level within 7 days of reinitiation
- Grade 3 neurologic event reoccurs at a dose of 9 $\mu\text{g}/\text{day}$
- Grade 4 neurologic event
- A second seizure occurs after reinitiation of blinatumomab at any dose

Elevated Liver Enzymes

- Total bilirubin (TBL) $> 2 \times$ ULN OR international normalized ratio (INR) > 1.5 (for subjects not on anticoagulant therapy) AND
- AST/ALT $> 3 \times$ ULN (when baseline was $< \text{ULN}$) AND
- No other cause of combination of the above laboratory abnormalities is immediately apparent

Other Clinical Relevant Adverse Events

- Initial grade 3 event does not improve to grade ≤ 1 within 14 days (with the exception of delay in restart due to logistical difficulties, in which case the restart may be postponed for an additional 7 days)
- Grade 3 event reoccurs at the lower dose level within 7 days of reinitiation
- Grade 3 event reoccurs at a dose of 9 $\mu\text{g}/\text{day}$ without prior dose-step escalation
- Dose limiting toxicities (DLTs) as described in [Section 6.2.2](#)

Subjects who permanently discontinue study treatment due to adverse event should continue with other study procedures, including response assessment, as appropriate.

6.2.2 Study Stopping Rules

The DLT evaluation period will be the entire duration of cycle 1 of blinatumomab treatment. For subjects who are removed from study treatment for reasons other than an adverse event/toxicity, ie, disease progression, they will be considered DLT evaluable if they have received at least 7 days of the target dose of blinatumomab.

The occurrence of any of the following toxicities will be considered a DLT, if judged by the investigator to be related to blinatumomab administration:

- grade 5 toxicity
- grade 4 non-hematologic toxicity (non-laboratory)
- grade 4 hematologic toxicity lasting ≥ 7 days (**excluding lymphopenia**)
- grade 4 laboratory abnormalities lasting ≥ 7 days (**excluding lymphopenia**)
- any permanent discontinuation of blinatumomab as described in [Section 6.2.1.3](#)

The stopping rules will use a Bayesian approach to terminate the study if the posterior probability that the DLT rate is greater than 25% is $> 90\%$ ([Section 10.3.1](#)).

6.3 Other Protocol-required Therapies

All other protocol-required therapies including, dexamethasone, that are commercially available are not provided or reimbursed by Amgen (except if required by local regulation). The investigator will be responsible for obtaining supplies of these protocol-required therapies.

Additional details regarding these protocol-required therapies are provided in the IPIM.

6.3.1 Dexamethasone Premedication

Mandatory premedication with dexamethasone is required before the treatment cycle and at each dose-step for the prevention of CRS and neurologic events resulting from blinatumomab treatment. Dexamethasone premedication will also be required before restarting blinatumomab after a dose interruption due to an adverse event or technical/logistical issue. Refer to [Table 2](#) for details. Collect dose, unit, frequency, route, start date, stop date and reason for dose change.

Table 2. Dexamethasone Pre-dose Treatment and for Events

Treatment Phase	Target Subjects	Dexamethasone Dose
Pre-dose dexamethasone prior to blinatumomab treatment cycle and before each dose-step increase	All subjects assigned to treatment	Dexamethasone 20 mg IV: within 1 hour prior to start of treatment in treatment cycle, and within 1 hour prior to dose-step increase.
Infusion interruption/dose modification due to adverse event or interruption due to technical/logistical event	Subjects who interrupt treatment > 4 hours	Dexamethasone 20 mg IV: within 1 hour prior to restart of treatment
In case of signs of CRS	Subjects with signs of CRS	Dexamethasone orally or IV at a dose maximum of 3 doses of 8 mg/day (24 mg/day) for up to 3 days. The dose should then be reduced step-wise over 4 days.
Infusion interruption/dose modification due to neurologic events	Subjects with neurologic event	Dexamethasone should be administered at a dose of at least 24 mg/day for up to 3 days. Dexamethasone will then be reduced step-wise over 4 days.

CRS = cytokine release syndrome; IV = intravenous

6.4 Hepatotoxicity Stopping and Rechallenge Rules

Subjects with abnormal hepatic laboratory values (ie, alkaline phosphatase [ALP], AST, ALT, TBL) and/or international normalized ratio [INR] and/or signs/symptoms of hepatitis (as described below) may meet the criteria for withholding or permanent discontinuation of Amgen investigational product or other protocol-required therapies as specified in the Guidance for Industry Drug-Induced Liver Injury (DILI): Premarketing Clinical Evaluation, July 2009.

6.4.1 Criteria for Withholding and/or Permanent Discontinuation of Amgen Investigational Product and Other Protocol-required Therapies Due to Potential Hepatotoxicity

The following stopping and/or withholding rules apply to subjects for whom another cause of their changes in liver biomarkers (TBL, INR and transaminases) has not been identified.

Important alternative causes for elevated AST/ALT and/or TBL values include, but are not limited to:

- Hepatobiliary tract disease
- Viral hepatitis (eg, Hepatitis A/B/C/D/E, Epstein-Barr Virus, cytomegalovirus, Herpes Simplex Virus, Varicella, toxoplasmosis, and Parvovirus)

- Right sided heart failure, hypotension or any cause of hypoxia to the liver causing ischemia.
- Exposure to hepatotoxic agents/drugs or hepatotoxins, including herbal and dietary supplements, plants and mushrooms
- Heritable disorders causing impaired glucuronidation (eg, Gilbert's Syndrome, Crigler-Najjar syndrome) and drugs that inhibit bilirubin glucuronidation (eg, indinavir, atazanavir)
- Alpha-one antitrypsin deficiency
- Alcoholic hepatitis
- Autoimmune hepatitis
- Wilson's disease and hemochromatosis
- Nonalcoholic Fatty Liver Disease including Steatohepatitis (NASH)
- Non-hepatic causes (eg, rhabdomyolysis, hemolysis)

If investigational product(s) is/are withheld, the subject is to be followed according to recommendations in [Appendix A](#) for possible DILI.

Rechallenge may be considered if an alternative cause for impaired liver tests (ALT, AST, ALP) and/or elevated TBL, is discovered and the laboratory abnormalities resolve to normal or baseline ([Section 6.4.2](#)).

Table 3. Conditions for Withholding and/or Permanent Discontinuation of Amgen Investigational Product and Other Protocol-required Therapies Due to Potential Hepatotoxicity

Analyte	Temporary Withholding	Permanent Discontinuation
TBL	> 3 x ULN at any time	> 2 x ULN
		OR
INR	--	> 1.5 (for subjects not on anticoagulation therapy)
	OR	AND
AST/ALT	> 8 x ULN at any time > 5 x ULN but < 8 x ULN for ≥ 2 weeks > 5 x ULN but < 8 x ULN and unable to adhere to enhanced monitoring schedule > 3 x ULN with clinical signs or symptoms that are consistent with hepatitis (such as right upper quadrant pain/tenderness, fever, nausea, vomiting, jaundice).	In the presence of no important alternative causes for elevated AST/ALT and/or TBL values > 3 x ULN (when baseline was < ULN)
	OR	
ALP	> 8 x ULN at any time	--

ALP = alkaline phosphatase; ALT = alanine aminotransferase; AST = aspartate aminotransferase; INR = international normalized ratio; TBL = total bilirubin; ULN = upper limit of normal

6.4.2 Criteria for Rechallenge of Amgen Investigational Product and Other Protocol-required Therapies After Potential Hepatotoxicity

If signs or symptoms recur with rechallenge, then blinatumomab and other protocol-required therapies, as appropriate should be permanently discontinued.

Subjects who clearly meet the criteria for permanent discontinuation (as described in [Table 3](#)) should never be rechallenged.

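### The protocol states no restart rule for a liver withholding with no alternative cause, and a related one that is never resumed can stay in the DLT denominator without counting as a DLT

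*Protocol*

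**What the plan says.** **Withholding.** The liver row of protocol Table 1 (Section 6.2.1.2.2) begins "Interrupt blinatumomab (refer to Table 3) if any one of the following occurs". One of its triggers is "AST or ALT > 8x ULN at any time". Table 3 (Section 6.4.1) places these triggers in its temporary column. The CRS, neurologic and other-event rows of Table 1 each give a minimum time and a dose level for restarting. The liver row gives neither and refers to Table 3 and Section 6.4.

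**Restart.** Section 6.4.1 says that its rules "apply to subjects for whom another cause of their changes in liver biomarkers (TBL, INR and transaminases) has not been identified". Its one statement on resuming is "Rechallenge may be considered if an alternative cause for impaired liver tests (ALT, AST, ALP) and/or elevated TBL, is discovered"; it adds that the abnormal values must have returned to normal or to the subject's baseline. Section 6.4.2 requires permanent discontinuation if signs or symptoms recur on rechallenge, and rules out rechallenge for subjects who clearly meet the permanent criteria of Table 3.

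**Permanent discontinuation.** Under elevated liver enzymes, Section 6.2.1.3 lists one combined criterion: bilirubin above 2 x ULN or INR above 1.5, together with AST/ALT above 3 x ULN, and "No other cause of combination of the above laboratory abnormalities is immediately apparent". A separate entry for other clinically relevant events covers grade 3 events that have not improved to grade 1 or lower within 14 days.

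**DLT.** Section 6.2.2 counts, when the investigator judges them related, grade 5 events, certain grade 4 events (for laboratory abnormalities, those lasting at least 7 days, lymphopenia excluded), and "any permanent discontinuation of blinatumomab as described in" Section 6.2.1.3. Protocol Section 10.1.2.5 and SAP Section 6.5 keep a subject removed for toxicity in the DLT Analysis Set whether or not a DLT was scored.

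**The concern.** The restart condition and the scope of the rules do not meet. The withholding rules address subjects with no other cause identified, while rechallenge is described only where another cause is later discovered. For a subject in whom none is ever found, the text labels the withholding temporary but does not say how it ends.

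If it ends treatment, it works as a permanent discontinuation for toxicity without being on the list that Section 6.2.2 uses. The recurrence rule in Section 6.4.2 has the same problem more plainly: it mandates permanent discontinuation, and Section 6.2.1.3 does not name it.

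The Bayesian rule in protocol Section 10.3.1 and SAP Section 7.1 is the trial's formal safety brake. It works on small counts, so a related, treatment-ending event that enters the denominator but not the numerator makes the brake less sensitive. About 30 treated subjects are planned over approximately 35 sites, so each site will see few cases and may settle the ambiguity differently.

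**Working it through.** **1. Which events fall in the gap.** The grades are those of SAP Table 14-1.

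| Liver event, judged related | DLT as written? |
|---|---|
| Combined bilirubin/INR plus transaminase criterion | Yes, listed in 6.2.1.3 |
| Grade 4 laboratory abnormality for at least 7 days | Yes, 6.2.2 |
| Grade 5 event | Yes, 6.2.2 |
| Grade 3 not improved to grade 1 or lower within 14 days | Unclear: depends on whether the other-events entry covers liver events |
| AST/ALT > 8 to 20 x ULN, or bilirubin > 3 to 10 x ULN (both grade 3), resolving within 14 days, combined criterion not met, never resumed | No criterion applies |
| AST/ALT > 3 x ULN with hepatitis symptoms, resolving within 14 days, combined criterion not met, never resumed | No criterion applies |
| Recurrence after rechallenge, stopped under 6.4.2 | Not by the discontinuation criterion, unless it also meets a row above |

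**2. The unclear row.** Suppose the other-events entry does cover liver events. AST/ALT above 5 x but below 8 x ULN for 2 weeks or more is grade 3 and has not improved to grade 1 or lower within 14 days. Section 6.2.1.3 would make that a permanent discontinuation, while Tables 1 and 3 make it temporary. Suppose instead the entry does not cover liver events. Then the conflict disappears, but persistent isolated grade 3 liver events join the gap. Neither reading makes the sections agree.

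**3. Reproducing the boundary.** Inputs from protocol Section 10.3.1: prior Beta(0.5, 1.5), DLT limit 25%, stop if the posterior probability exceeds 90%, batches of 10. With r DLTs among n subjects, the posterior is Beta(0.5 + r, 1.5 + n - r).

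| r/n | Posterior | P(rate > 25%) | Decision |
|---|---|---|---|
| 4/10 | Beta(4.5, 7.5) | 0.812 | continue |
| 5/10 | Beta(5.5, 6.5) | 0.935 | stop |
| 7/20 | Beta(7.5, 14.5) | 0.814 | continue |
| 8/20 | Beta(8.5, 13.5) | 0.913 | stop |

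This agrees with Table 7 (at least 5 of 10, at least 8 of 20). It also shows that one uncounted case can change the decision at either look.

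**4. Reproducing the operating characteristics.** Let X1 and X2 be the DLT counts in the first and second batches of 10, each binomial with rate p.

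P(stop) = P(X1 ≥ 5) + Σ (x = 0 to 4) P(X1 = x) · P(X2 ≥ 8 - x)

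- p = 0.35: 0.2485 + 0.1969 = 0.4454
- p = 0.30: 0.1503 + 0.1226 = 0.2729
- p = 0.25: 0.0781 + 0.0585 = 0.1366

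Over rates 0.20, 0.25, 0.30, 0.35 and 0.40 the results are 5.2%, 13.7%, 27.3%, 44.5% and 62.3%. Table 8 prints 5%, 14%, 27%, 44% and 62%. Tables 7 and 8 are sound; the question is which events enter them.

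**5. Effect of missed events.** The documents give no rate for the events in the gap, so the missed share is an assumption, shown as a range. The full rate means DLTs as now defined plus related liver events that ended treatment but met no DLT criterion. The counted rate is the full rate minus the missed share, and the formula in step 4 is applied to it.

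| Full rate | None missed | 2 points missed | 5 points missed | 10 points missed |
|---|---|---|---|---|
| 30% | 27.3% | 21.3% | 13.7% | 5.2% |
| 35% | 44.5% | 37.4% | 27.3% | 13.7% |
| 40% | 62.3% | 55.4% | 44.5% | 27.3% |

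**The case against.** The strongest reply is that the text is silent here rather than contradictory. Section 6.4.1 says when rechallenge may be considered; it does not say that this is the only case. Section 6.4.2 reserves its absolute bar for the permanent criteria, and Appendix A distinguishes permanent from conditional withholding. The paragraph after Table 1 describes how any infusion is restarted after an adverse event. A reader might infer that a withheld subject without an alternative cause cannot resume. The documents do not support that: no passage forbids it. What stands is that no passage states when it may happen.

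A reader might also infer that all liver toxicity that ends treatment escapes the DLT count. That is too broad. The combined criterion, lasting grade 4 laboratory abnormalities and grade 5 events are DLTs when judged related. Section 9.2.2.1 requires grade 3 and 4 laboratory values to be recorded as adverse events, so persistent grade 3 events may be caught by the other-events entry. Nor are events in the gap automatically related to blinatumomab. An unidentified cause is not a finding of relatedness, and Section 6.2.2 leaves that judgement to the investigator.

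Finally, oversight does not rest on the DLT count alone. The Data Review Team sees adverse events as well as DLTs, evaluations may be brought forward for emerging concerns, and adverse events leading to withdrawal are tabulated. This softens the consequence but does not define the count on which the formal rule depends. That one borderline case can decide a look is true of any DLT definition; it is a reason to make this one unambiguous.

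**Conclusion.** The point holds in a limited form. No restart rule is stated for a liver withholding without an alternative cause. A related withholding that is never resumed, and a discontinuation required by Section 6.4.2, are not DLTs by the discontinuation criterion, although the subject stays in the denominator. The gap is mainly isolated events of grade 3 or lower that resolve within 14 days. Whether it also includes persistent grade 3 events depends on an entry whose scope is unclear and which, if it applies, conflicts with the temporary label.

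The size is conditional. With 2 to 10 percentage points missed from an assumed full rate of 35%, the probability of stopping falls by about 7 to 31 percentage points (44.5 - 37.4 = 7.1; 44.5 - 13.7 = 30.8). The loss is small if such events are rare, and nothing in the documents says how common they are. The calculation assumes looks at exactly 10 and 20 evaluable subjects, events judged related, and no other DLT in the affected subjects. This should be corrected, but it does not undermine the stopping boundary itself.

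**What to change.** - Reconcile Table 1, Table 3 and Sections 6.2.1.3, 6.4.1 and 6.4.2 so that one consistent text says whether and when a liver withholding with no alternative cause is temporary or permanent. The same text should say whether the other-events entry in Section 6.2.1.3 applies to liver events. Which clinical rule is right is for the sponsor to decide; none is proposed here.
- Align Section 6.2.2 and SAP Section 6.5 with the result. Any protocol-mandated or actual permanent end of treatment for liver toxicity that the investigator judges related should count for the stopping rule in the same way as the discontinuations listed in Section 6.2.1.3. This includes discontinuation on recurrence under Section 6.4.2.

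The cost is a clarification in the next protocol amendment and a matching SAP edit. The boundary and operating characteristics need no recalculation. The observed DLT rate may rise slightly, and with it the chance of reaching the boundary.
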